All subjects will continue smoking their single preferred brand of CC *ad libitum*. Twenty four-urine will be collected starting in the morning of the Day -2 finishing in the morning of the Day -1, and starting in the morning of the Day -1 finishing in the morning of Day 1. During Day -1, spirometry and CYP2A6 blood sampling have to be done prior to smoking.

On Day -1, subjects will be randomized to 1 of the 2 study arms in a 1:1 ratio using a stratified randomization:

- CHTP 1.0 arm: ~ 40 subjects, *ad libitum* use of CHTP 1.0.
- CC arm: ~ 40 subjects, *ad libitum* use of CC.

Subjects will be informed of their randomized study arm by the site collaborators on Day 1 prior to 06:30 AM (the start of the Exposure Period). Subjects who do not complete the study after randomization will not be replaced.

- Exposure Period (from Day 1, 06:30 AM until Day 5, 11:00 PM):

The exposure period will consist of 5 days of exclusive *ad libitum* use of the assigned product (CHTP 1.0 or CC) between 06:30 AM and 11:00 PM.

Subjects in the CC and CHTP 1.0 arms who are willing to attempt quitting smoking during the study will be encouraged to do so and will be referred to appropriate medical service.

Use of any tobacco/nicotine containing product other than the assigned product will not be allowed throughout the Exposure Period and may, at the discretion of the Investigator, result in the subject's discontinuation from the study.

Twenty four-hour urine will be collected from Day 1 to Day 5 on site to measure BoExp. On Day 1, product use must not start prior to the end of urine collection of Day -1. The end

Confidentiality Statement

Data and information contained in this document are considered to constitute trade secrets and confidential commercial information, and the legal protections provided to such trade secrets and confidential information are hereby claimed under the provisions of applicable law. No part of this document may be publicly disclosed without the written consent of Philip Morris Products S.A.

of the 24-h urine collection period for Day 5 will end in the morning of Day 6 prior to Discharge.

- Day of Discharge (Day 6) (from Day 5, 11:01 PM to Discharge):

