Procedures of Discharge including but not limited to laboratory parameters will be conducted to discharge the subject from the clinic after 9 days in a confined setting. Use of CC will be allowed on Day 6 but only after 24-h urine collection is completed, and spirometry and CYP2A6 blood sampling have been performed.

- Safety Follow-up Period (from Discharge on Day 6 to Day 13):

After Discharge, the subject will enter a 7-day Safety Follow up Period during which the follow-up of ongoing AEs/SAEs will be done by the study site. All AEs will be followed-up until resolved, stabilized (i.e., no worsening of the event), or a plausible explanation for the event has been found until the end of the Safety Follow-up Period. Within 3 days after the end of the Safety Follow-up Period the investigator will attempt to contact the subjects by phone to check for if all AEs/SAEs potentially occurring during the Safety Follow-up Period are fully reported.

The end of the study for a subject is defined as Discharge on Day 6 or the date of early termination of the subject plus the 7 days for the Safety Follow-up Period plus up to 3 days to ensure that all AEs/SAEs potentially occurring during the Safety Follow-up period are fully reported.

If the investigator can reach the subject by phone within 3 days after the end of the Safety Follow-up Period, the date of this phone call with the subject will be recorded as the date of the end of the study of the subject. If the investigator cannot reach the subject by phone within 3 days after the end of the Safety Follow-up Period, the date of the last contact (e.g., last visit of the subject, last phone call with the subject) will be recorded as the date of the end of the study of the subject.

The EOS of the entire study is the end of the Safety Follow-up Period plus up to 3 days of the last subject.

At the end of the Safety Follow-up Period, all ongoing AEs will be documented as “ongoing” and will not be followed-up by the Investigator. At the discretion of the Investigator, the subject will be referred to his General Practitioner for follow up on ongoing AEs.

Confidentiality Statement

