6.3.4 Day of Discharge (Day 6)

Use of CC will be allowed on Day 6 but only after twenty four-hour urine collection of Day 5 is completed, and spirometry and CYP2A6 blood sampling have been performed.

Confidentiality Statement

Data and information contained in this document are considered to constitute trade secrets and confidential commercial information, and the legal protections provided to such trade secrets and confidential information are hereby claimed under the provisions of applicable law. No part of this document may be publicly disclosed without the written consent of Philip Morris Products S.A.

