6.6.3 Investigational Product Retention

Used and unused CHTP 1.0 will be destroyed or returned to the Sponsor upon study completion as per instructions which will be provided by the Sponsor in due time.

Irrespective of the study arm, at Discharge from the site, the site staff will return to the subjects any remaining CCs given by them on the Day of Admission.

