7.3.8 Vital Signs

Systolic and diastolic blood pressure, pulse rate and respiratory rate will be measured in the morning at applicable visits. All measurements will be made after the subject has rested for at least 5 minutes in a supine position.

For every measurement of vital signs, it has to be ensured and documented that the duration between the end of last smoking and the measurement should be at least 15 minutes.

See [Appendix A](#) for the timepoints of assessment.

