Start of Procedure		Day 6	
		AE/SAE recording	At any time of the day
		Concomitant medications	At any time of the day
		End of 24-hour urine sample collection for Day 5	The urine is collected for 24 hours \pm 1 hour.
		Urine sample to be taken from the 24-hour urine of Day 5	Aliquots from 24-hour urine will be collected according to Table A2. Bio-banking for biomarkers (if additional consent is obtained)
06:29 AM \pm 30 min	√	Clinical laboratory parameters (hematology, clinical chemistry)	After at least 10 hours of fasting
06:29 AM \pm 30 min	√	CYP2A6 activity in plasma	Has to be done before smoking
Before Discharge		Spirometry pre- and post-bronchodilator (recording of FEV ₁ , FVC, FEV ₁ /FVC)	Has to be done before smoking At rest in sitting position for at least 15 minutes prior to pulmonary function testing In sitting position All post-bronchodilator spirometry testing will be performed 15-30 minutes post administration of salbutamol
06:29 AM \pm 1 hour		MNWS questionnaire	
06:29 AM \pm 1 hour		Assessment of cough (VAS)	

Confidentiality Statement

Data and information contained in this document are considered to constitute trade secrets and confidential commercial information, and the legal protections provided to such trade secrets and confidential information are hereby claimed under the provisions of applicable law. No part of this document may be publicly disclosed without the written consent of Philip Morris Products S.A.

Time	Blood Sample	Procedures	Additional Information
Start of Procedure		Day 6	
Prior to 11:30 AM	√	Bio-banking for biomarkers, transcriptomics and lipidomics	If additional consent is signed After at least 10 hours of fasting
Before Discharge		Vital signs (blood pressure, pulse rate, respiratory rate)	At least 5 minutes in supine position
Before Discharge		Physical examination, body weight, and calculated BMI	
Before Discharge		Safety urine analysis	
Before Discharge		Urine pregnancy test (females only)	
Before Discharge		ECG	At least 10 minutes in supine position prior to recording
Before Discharge		Information on the risks of smoking, smoking cessation advice and debriefing.	
		Discharge	

Abbreviations: AE = Adverse event; BMI = Body mass index; BoExp = Biomarker (s) of exposure; CC = Conventional cigarette(s); CYP2A6 = Cytochrome P450 2A6; FEV₁ = Forced expiratory volume in 1 second; FVC = Forced vital capacity; MNWS = Minnesota nicotine withdrawal scale (revised version); SAE = Serious adverse event

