Procedures of Discharge including but not limited to laboratory parameters will be conducted to discharge the subject from the clinic. Use of CC will be allowed on Day 6 but only after twenty four-hour urine collection is completed, and spirometry and CYP2A6 blood sampling have been performed.

[figure not shown]
6) The Safety Follow-up Period (from Discharge on Day 6 to Day 13):

After Discharge, the subject will enter a 7-day Safety Follow up Period during which the follow-up of ongoing AEs/SAEs will be done by the study site. All AEs will be followed-up until resolved, stabilized (*i.e.*, no worsening of the event), or a plausible explanation for the event has been found until the end of the Safety Follow-up Period. Within 3 days after the end of the Safety Follow-up Period the investigator will attempt to contact the subjects by phone to check for if all AEs/SAEs potentially occurring during the Safety Follow-up period are fully reported. At the end of the Safety Follow-up Period, all ongoing AEs will be documented as “ongoing” and will not be followed-up by the Investigator. At the discretion of the Investigator, the subject will be referred to his General Practitioner for follow up on ongoing AEs.

The end of the study for a subject is defined as Discharge on Day 6 or the date of early termination of the subject plus the 7 days for the Safety Follow-up Period plus up to 3 days to ensure that all AEs/SAEs potentially occurring during the Safety Follow-up period are fully reported.

If the investigator can reach the subject by phone within 3 days after the end of the Safety Follow-up Period, the date of this phone call with the subject will be recorded as the date of the end of the study of the subject. If the investigator cannot reach the subject by phone within 3 days after the end of the Safety Follow-up Period, the date of the last contact (e.g., last visit of the subject, last phone call with the subject) will be recorded as the date of the end of the study of the subject.

The EOS of the entire study is the end of the Safety Follow-up Period plus up to 3 days of the last subject.

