12.5.4.5.5 Electrocardiogram

The ECG data will be obtained directly from the 12-lead ECG traces, i.e. not centrally read. These data include the PR, QT, and QT interval corrected using Bazett's formula (QTcB) and using Fridericia's formula (QTcF) intervals; QRS duration; and heart rate; and normality evaluation (normal, abnormal, clinically relevant, together with any PMI comments to the abnormality).

The baseline for the ECG data will be the Screening value.

ECG data values and normality evaluations will be listed by product and study day (Screening and Day 6) together with changes from baseline and shift in normality. ECG data from subjects which had significant clinical findings will be flagged in listings.

Descriptive statistics will be presented for ECG data at baseline, and Day 6 by product. ECG data will be summarized together with changes from baseline, and the number and percentage of subjects with normal/abnormal/abnormal clinically significant results.

The data will be presented in the below outputs, the TFL number refers to the TFL number in the accompanying TFL shell document:

TFL number	Title
TABLES	
15.2.6.17	Summary of ECG Measurements – Safety Population
LISTINGS	
15.3.6.9	Listing of ECG Data and Changes from Baseline

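### Cigarettes are permitted on Day 6 before the discharge ECG, vital signs and bio-banking blood are taken, so CHTP-arm readings can follow comparator use

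*Protocol*

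**What the plan says.** Protocol section 6.3.4 sets the Day 6 smoking rule: "Use of CC will be allowed on Day 6 but only after twenty four-hour urine collection of Day 5 is completed, and spirometry" and the CYP2A6 blood sample are finished. Section 4.1 repeats it ("Use of CC will be allowed on Day 6 but only after 24-h urine collection is completed, and spirometry and CYP2A6 blood sampling"), as do the synopsis and section 6.7.1. SAP section 6.1 carries the same three conditions and adds none ("Use of CC will be allowed on Day 6 but only after twenty four-hour urine collection is completed, and spirometry and CYP2A6 blood sampling"). Section 4.1 defines the period as "Day of Discharge (Day 6) (from Day 5, 11:01 PM to Discharge", so the permission operates inside the clinic. It is not restricted to one arm.

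Table 15 marks two Day 6 procedures as having to be done before smoking: spirometry and CYP2A6. The ECG is due before Discharge with one stated condition: "At least 10 minutes in supine position prior to recording". Vital signs are also due before Discharge, after 5 minutes supine; section 7.3.8 adds that "the duration between the end of last smoking and the measurement should be at least 15 minutes". Bio-banking blood is due before 11:30 AM, fasting, with consent.

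Table A1 schedules the ECG at Screening and Day 6 only. SAP section 12.5.4.5.5 takes Screening as the ECG baseline and says: "Descriptive statistics will be presented for ECG data at baseline, and Day 6 by product".

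On access to cigarettes, section 6.6.1 describes CC dispensing from Day -3 to Day 5, and section 6.6.3 says that "at Discharge from the site, the site staff will return to the subjects any remaining CCs given by them" on the day of Admission.

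**The concern.** The protocol protects spirometry and an exploratory enzyme ratio from smoking on the morning of Day 6. It does not protect the ECG or discharge vital signs, which are secondary safety endpoints, or the post-exposure banked blood. The Day 6 permission is for CC, so in the CHTP arm any smoking that morning is use of the comparator. A reading taken afterwards can no longer be attributed to five days of CHTP 1.0, yet the SAP reports it under that product and has no rule to flag or handle it. This matters most for the ECG, because a completer has no other scheduled ECG after exposure, and because the protocol (section 2.1.2) states that no clinical study had yet been done with CHTP 1.0.

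**Working it through.** The plan gives no figure to reproduce. The check compares the Day 6 rule with each procedure's own conditions and then does clock arithmetic on the stated windows.

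**Side by side (Table 15, with sections 6.3.4, 7.3.8, 7.3.9.2 and Table A1 footnote c)**

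| Day 6 item | Timing | Must precede smoking? |
|---|---|---|
| End of Day 5 urine | 24 h ± 1 h | Yes (6.3.4) |
| CYP2A6 blood | 06:29 AM ± 30 min | Yes (6.3.4, Table 15, footnote c) |
| Spirometry | before Discharge | Yes (6.3.4, Table 15, footnote c) |
| ECG | before Discharge | No; 10 min supine |
| Vital signs | before Discharge | No; 5 min supine, 15 min since last smoking |
| Bio-banking blood | before 11:30 AM | No; 10 h fasting |

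Section 6.7.1 also bars product use during study procedures. That stops smoking while a procedure is under way; it does not put the procedure ahead of the first cigarette.

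**When CC can be unlocked**

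- CYP2A6 window closes: 06:29 + 0:30 = 06:59 AM.
- Urine collection ends shortly before 06:29 AM (section 7.6.2), or at the edge of its window: 06:29 + 1:00 = 07:29 AM.
- Spirometry has no clock time. Assume it is finished by then. All three conditions are then met between 06:59 and 07:29 AM.

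**Permitted smoking time before the bio-banking deadline**

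- 11:30 − 06:59 = 4 h 31 min.
- 11:30 − 07:29 = 4 h 01 min.
- If spirometry is later, the interval shrinks; it is zero if spirometry follows the draw.

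For the ECG and vital signs the interval is open up to Discharge, limited only by the 15-minute gap for vital signs.

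**State of both arms without Day 6 smoking**

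- Product use ends at 11:00 PM on Day 5 (section 6.3.3). From 11:00 PM to 06:30 AM is 7.5 h.
- Appendix D gives a plasma nicotine half-life of 1 to 2 h: 7.5/2 = 3.75 and 7.5/1 = 7.5 half-lives.
- Fraction remaining: 2^−3.75 ≈ 7%; 2^−7.5 ≈ 0.5%.

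**Effect on the between-arm difference**

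Let d be the Day 6 difference (CHTP − CC) with nobody smoking first, e the acute effect of a recent cigarette on the reading (assumed equal in both arms), and f_CHTP and f_CC the fractions who smoke first. The observed difference is then about d + (f_CHTP − f_CC) × e. The documents give none of these quantities. The added term vanishes if the fractions are equal and can take either sign.

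**Primary endpoints**

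COHb is drawn around 8:00 PM on Day 5, and the Day 5 urine must be complete before any Day 6 cigarette. Neither can be affected.

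**The case against.** The strongest reply is that this is unlikely to happen. Cigarettes are in secured storage (6.6.2), subjects have no free access (6.7.1), dispensing is described only to Day 5 (6.6.1), and packs go back at Discharge (6.6.3). The amendment log's reason for freeing the spirometry time was that no product would be used on the Discharge Day. Spirometry shares the open before-Discharge window, so a site may well run the ECG and vital signs alongside it, before any cigarette. All of this stands as evidence of intent and of low likelihood. It does not cancel a permission written in five places; it shows that the sections disagree.

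The second reply is that little is at stake: the primary endpoints are safe, vital signs are also taken on every exposure day, the Day 6 summaries are descriptive, bio-banking is optional with no SAP endpoint, and early terminators have an ECG of their own. This also stands, and it limits the point to Day 6 safety readings and banked blood.

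Three stronger readings are tempting and are not supported:

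- A reader might infer that the Day 6 difference is diluted in proportion to the CHTP subjects who smoke first. That ignores smoking in the CC arm, and it presumes an acute product difference that overnight abstinence has largely removed in both arms.
- A reader might infer that contamination runs only one way. CC-arm readings also depend on whether they come before or after a cigarette.
- A reader might call this the only on-product ECG. After 7.5 hours off product it is a post-exposure ECG.

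Nor is it certain that Day 6 smoking would go unlogged. Table A1 collects no butts that day, but section 6.6.1 also asks for dispensing and return times on each confinement day. Logging is unclear, not excluded.

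Finally, the SAP analyses safety by actual exposure. That does not settle the matter: it provides only CHTP and CC labels and no rule for a CHTP subject who smoked permitted CC on Day 6.

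**Conclusion.** The gap is real on the text. A site following the protocol can record a CHTP completer's only scheduled post-exposure ECG, the discharge vital signs and the bio-banking blood after comparator use, and the SAP would summarise the ECG and vital signs as CHTP. One of one scheduled post-exposure ECGs is open to this in up to about 40 CHTP subjects. The number actually affected, and the size and direction of any shift, cannot be derived from the documents. The 4 h 01 min to 4 h 31 min interval assumes early spirometry; the half-life calculation covers nicotine only. The primary endpoints are unaffected. The correction is worth making because the loss of attribution is avoidable and the remedy changes only the order of assessments.

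**What to change.** 1. In Table 15 and in the Day 6 lists (synopsis, sections 4.1, 6.3.4 and 6.7.1, and SAP section 6.1), give the Day 6 ECG, vital signs and bio-banking blood the same before-smoking condition that spirometry and CYP2A6 sampling carry.
2. Reconcile section 6.3.4 with sections 6.6.1 and 6.6.3 on whether CC is available before Discharge.
3. Record any CC smoked on Day 6 before Discharge, with times, and have the SAP flag readings taken afterwards. If the Day 6 visits are already complete, flag from whatever times were recorded.
4. For MNWS and cough, no more is needed than aligning Table 15 with SAP section 7.2.4, which has MNWS completed before product use. Both recall the previous 24 hours and are timed at 06:29 AM ± 1 hour.

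The cost is wording, a log entry and possibly a later first cigarette; there is no added procedure, visit or sample. There is one analytic downside. The Screening ECG and the Day -1 vital signs are not tied to smoking, so change from baseline will include overnight abstinence in both arms. The between-arm comparison stays like for like, and the report should say so when it presents within-arm changes.

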6.3.5 Safety Follow-up Period

During the Safety Follow-up Period (after discharge at Day 6 until Day 13), all subjects are free to smoke their own CC *ad libitum*.

6.3.6 Stopping Rules for Investigational Product

For safety purposes, smoking should be temporarily stopped in the event of any signs suggesting nicotine overexposure, (e.g., gastrointestinal disturbance [nausea, vomiting, diarrhea, stomach or abdominal pain], cold sweats, headache, dizziness, and breathing problems) or any reasons at the discretion of the Investigator or designee.

6.4 Method for Assigning Subjects to Study Arms

When all the eligibility criteria have been met, randomization will be done through the interactive web and voice response system (IxRS) on Day -1 at any time during the day. Subjects will be informed of their randomized study arm in the morning of Day 1, prior to 06:30 AM (the start of the Exposure Period). Subjects will be randomized to one of the 2 study arms: CHTP 1.0:CC in a 1:1 ratio.

Stratified randomization will be conducted by sex and by average daily CC consumption over the last 6 weeks prior to Admission as self-reported (smokers smoking 10 to 19 CC/day and smokers smoking > 19 CC/day). In each arm, each sex and each of the smoking strata should have a quota applied to ensure they represent at least 40% of the population.

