SAE	Serious adverse event
SAP	Statistical analysis plan
SHM	Sample handling manual
SOP	Standard operating procedure
SRO	Subject reported outcome(s)
T	Time point

Confidentiality Statement

Data and information contained in this document are considered to constitute trade secrets and confidential commercial information, and the legal protections provided to such trade secrets and confidential information are hereby claimed under the provisions of applicable law. No part of this document may be publicly disclosed without the written consent of Philip Morris Products S.A.

T ₀	Time point of first product use during study day
t _½	Half-life
█	█
ULN	Upper limit of the normal range
ULOQ	Upper limit of quantification
VAS	Visual analogue scale
WBC	White blood cell (count)
WHO	World Health Organization

Confidentiality Statement

Data and information contained in this document are considered to constitute trade secrets and confidential commercial information, and the legal protections provided to such trade secrets and confidential information are hereby claimed under the provisions of applicable law. No part of this document may be publicly disclosed without the written consent of Philip Morris Products S.A.

Explanation of Terms

The following special terms are used in this protocol:

Conventional cigarette (CC)	The term ‘conventional cigarette’ refers to commercially available cigarettes (manufactured) and excludes cigars, pipes, bidis, and other nicotine-containing products.
Carbon Heated Tobacco Product 1.0 (CHTP 1.0)	CHTP 1.0 is a non-menthol tobacco stick which is comparable in shape and form, and is used in a similar manner to a conventional cigarette.
End of study (EOS)	The EOS for a subject is defined as Discharge on Day 6 or the date of early termination of the subject plus the 7 days for the Safety Follow-up Period plus up to 3 days to ensure that all AEs/SAEs potentially occurring during the Safety Follow-up period are fully reported. The EOS of the entire study is the end of the Safety Follow-up Period plus up to 3 days of the last subject.
Randomization	Allocation of the respective product at any time on Day -1 utilizing an interactive web and voice response system (IxRS). On Day 1, the subjects will be individually informed about the product they are randomized to prior to the first product use.

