6.5 Blinding

This is an open-label study; therefore the subjects and Investigators or designees will be unblinded to the subject's arm. However, there will be a limited degree of blinding in the data review and data analysis process. In particular, PMI and contract research organization (CRO) personnel will be blinded to the randomized arm as summarized in [Table 1](#):

Table 1 Description of Blinded Study Personnel

Blinded Study Personnel	End of Blinding Period
PMI and CRO Study Statisticians	After the SAP finalization or the database lock ^a whichever comes last.
PMI Data Manager	After the finalization of PMI blind database review ^b .
PMI Clinical Scientist	After the finalization of PMI blind database review ^b . Can be actively un-blinded when appropriate.

^a Data will be accessible blinded to randomization arm and to product use by means of a dummy randomization or masking.

^b As part of the PMI quality control (QC) activity, data listings will be reviewed by the CRO and PMI before database lock, with no access to the randomization information. Full details will be available in the data review plan.

Confidentiality Statement

Data and information contained in this document are considered to constitute trade secrets and confidential commercial information, and the legal protections provided to such trade secrets and confidential information are hereby claimed under the provisions of applicable law. No part of this document may be publicly disclosed without the written consent of Philip Morris Products S.A.

Any PMI and CRO personnel who are not listed in the above table will be unblinded by default.

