Prior to 11:30 AM		Spirometry pre- and post-bronchodilator (recording of FEV ₁ , FVC, FEV ₁ /FVC)	Has to be done before smoking At rest in sitting position for at least 15 minutes prior to pulmonary function testing. In sitting position. All post-bronchodilator spirometry testing will be performed 15-30 minutes post administration of salbutamol
Prior to 11:30 AM	√	Bio-banking for biomarkers and transcriptomics and lipidomics	If additional consent is signed. After at least 10 hours of fasting
Prior to 11:30 AM	√	Clinical laboratory parameters (hematology, clinical chemistry)	After at least 10 hours of fasting
Prior to 11:30 AM		Safety urine analysis	
Prior to 11:30 AM		Intake of a cup of coffee made from 4.2 g (±10%) regular instant coffee; CAF content: 72 mg/2 g) with 150 ml ±10 ml water.	The time of intake of the cup of coffee must be recorded
04:00 PM - 06:00 PM	√	CYP1A2 activity in plasma	6 hours ±15 minutes after intake of the the cup of coffee .
In the evening prior to 9:00 PM (approx. 8:00 PM ± 1 hour)		CO breath test	Has to be done in conjunction with COHb blood sampling.
In the evening prior to 9:00 PM (approx. 8:00 PM ± 1 hour)	√	COHb in blood	Has to be done in conjunction with CO breath test.
In the evening prior to 9:00 PM (approx. 8:00 PM ± 1 hour)	√	Plasma nicotine and cotinine sample	Cotinine will be measured in the same assay as nicotine. No additional blood samples required.

Confidentiality Statement

Data and information contained in this document are considered to constitute trade secrets and confidential commercial information, and the legal protections provided to such trade secrets and confidential information are hereby claimed under the provisions of applicable law. No part of this document may be publicly disclosed without the written consent of Philip Morris Products S.A.

Time	Blood Sample	Procedures	Additional Information
Start of Procedure		Baseline Period (Day -1)	
8:00 PM-11:00 PM		Craving questionnaire (QSU brief)	
8:00 PM-11:00 PM		Product evaluation questionnaire (MCEQ)	
11:00 PM		End of smoking period	
6:30 AM-11:15 PM		Collection of used CC butts	For accountability
		Randomization	Day -1

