12.3.1 Full Analysis Set

The FAS consists of all the randomized subjects who had at least one post-randomization product use experience, if randomized to CHTP 1.0 or CC, and have at least one valid nonsafety assessment (CHTP 1.0, CC).

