6.3 Product Allocation and Blinding

6.3.1 Methods of Assigning Subjects to Product Arms

When all the eligibility criteria have been met, the subject will be enrolled on Day -3. Randomization will be done through [REDACTED] on Day -1 at any time during the day. Subjects will be randomized to one of the 2 study arms: CHTP 1.0:CC in a 1:1 ratio. Subjects will be informed of their randomized study arm in the morning of Day 1, prior to 06:30 AM (the start of the Exposure Period).

Stratified randomization will be conducted by sex and by average daily CC consumption over the last 6 weeks prior to Admission as self-reported (smokers smoking 10 to 19 CC/day and smokers smoking > 19 CC/day). In each arm, each sex and each of the smoking strata should have a quota applied to ensure they represent at least 40% of the population.

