12.1.4 Definitions for Statistical Data Analysis

The following definitions (**Table 19**) for statistical analyses/presentations will be used:

Table 19: Definition of terms for the statistical analysis

Term	Definition
Baseline Value	The last valid assessment prior to 06:30 AM on Day 1

For 24-hour urine collections, the collection sample will be labelled by the day in which the collection started. As an example if the 24-hour urine sample is collected from Day 5 to Day 6, it will be analyzed and reported as the Day 5 sample.

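### The allocation can be drawn, and seen by site staff, at any time on Day -1, before the baseline values used in the primary model are complete

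*Protocol*

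**What the plan says.** **Timing of randomisation.** Protocol 6.4 says that "randomization will be done through the interactive web and voice response system (IxRS) on Day -1 at any time during the day". The Randomization definition in the protocol's explanation of terms and SAP 6.3.1 give the same rule. Table 9 (Day -1) lists randomisation without a clock time, and Protocol section 9 allows a procedure without a start time at any time of that day.

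**Who knows, and when.** Protocol 6.5 says: "This is an open-label study; therefore the subjects and Investigators or designees will be unblinded to the subject's arm". Table 1 there lists the blinded roles (statisticians, data manager, clinical scientist), and none of them is at the site. Disclosure to the subject is held back: "Subjects will be informed of their randomized study arm in the morning of Day 1, prior to 06:30 AM". Under Protocol 4.1 it is the site collaborators who tell the subject.

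**Baseline.** SAP Table 19 defines it as "The last valid assessment prior to 06:30 AM on Day 1", and Protocol 12.1.2 agrees in substance. SAP 12.5.1.1 puts log(baseline) in the primary model with sex, consumption stratum and product.

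**Full analysis set.** Protocol 12.3.1 admits "all the randomized subjects who had at least one post-randomization product use experience" who also have a valid non-safety assessment. It does not tie that use to Day 1.

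**The concern.** An ANCOVA baseline should be fixed before anyone who could affect it knows the allocation. Here the call may be made in the morning of Day -1, while most of the measurements that form the four biomarker baselines are still to come. During those hours the site hands out cigarettes one at a time (Protocol 6.6.1), draws the evening blood sample and checks the urine collection.

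If knowledge of the arm moved the Day -1 level in one arm but not the Day 5 level, the adjustment would carry that movement into the treatment estimate. The quantities exposed are the adjusted percentage reduction, its 95% CI, and any comparison of these with the 50% evaluation criterion. COHb matters most: its baseline is a single evening sample, and it is the endpoint that limits power (88%, against more than 99% for the other three).

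**Working it through.** **1. Timeline (Protocol 9.2.2, Table 9 and Table 10; SAP Table 16)**

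| Event | Time |
|---|---|
| IxRS call permitted | any time on Day -1 |
| Baseline COHb sample | about 8:00 PM ± 1 hour, Day -1 |
| End of smoking | 11:00 PM, Day -1 |
| Baseline 24-hour urine (MHBMA, 3-HPMA, S-PMA) | morning of Day -1 to 06:29 AM ± 1 hour, Day 1 |
| Subject told the arm | before 06:30 AM, Day 1 |

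A daytime call precedes the COHb baseline. Any call on Day -1 precedes the end of the urine baseline. The ± 1 hour window also lets the final void fall after the subject has been told. Protocol 4.1 requires only that product use on Day 1 wait for the end of that collection.

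**2. The plan's own power figure**

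Inputs from Protocol 12.2 and SAP 8: COHb mean ratio 0.40, CV 0.32, 40 per arm, one-sided 2.5%, 50% criterion.

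- SD on the log scale = √ln(1 + 0.32²) = 0.3122
- SE = 0.3122 × √(2/40) = 0.0698
- ln(0.50/0.40)/SE = 0.2231/0.0698 = 3.20
- Power = 89.2% (normal) or 88.4% (noncentral t, 78 df). The stated 88% is reproduced.

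**3. What a baseline shift would do**

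The adjusted log ratio is the Day 5 difference minus b times the baseline difference, where b is the slope on log baseline. If the CHTP arm's Day -1 level moves by a fraction s and Day 5 is unaffected, the ratio is multiplied by (1 + s)^(-b). The reciprocal applies to a movement of equal log size the other way. Neither s nor b is given in the documents; the ranges below are assumptions.

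| s | b | Factor, CHTP baseline up | Factor, CHTP baseline down | COHb 0.40 becomes |
|---|---|---|---|---|
| 5% | 0.3 | 0.985 | 1.015 | 0.394 or 0.406 |
| 10% | 0.5 | 0.953 | 1.049 | 0.381 or 0.420 |
| 20% | 1.0 | 0.833 | 1.200 | 0.333 or 0.480 |

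In the middle row the reported COHb reduction would be 61.9% or 58.0% instead of 60%.

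**4. Against the written null (ratio 1; Protocol 12.4.4, SAP 12.5.1.2)**

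At the planned COHb ratio the effect is ln(1/0.40)/0.0698 = 0.9163/0.0698 = 13.1 SE. Even the largest shift in the table, taken against the product, leaves (0.9163 - 0.1823)/0.0698 = 10.5 SE.

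**5. Against the 50% criterion**

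For s = 10% and b = 0.5 the log shift is 0.5 × ln 1.1 = 0.0477, or 0.0477/0.0698 = 0.68 SE. With SE held fixed (normal approximation):

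- At a true COHb ratio of exactly 0.50, the 2.5% error becomes 1 - Φ(1.960 - 0.683) = 10.1%. In the other direction it is 1 - Φ(1.960 + 0.683) = 0.4%.
- At the planned ratio of 0.40, the 89.2% power becomes 97.2% or 71.0%.
- With CV 0.70 (MHBMA, S-PMA), the 2.5% error becomes about 5%.

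**The case against.** The strongest reply is that the protocol already blocks the obvious route. A reader might infer that a subject about to lose cigarettes would smoke more that evening. That subject is not to be told until Day 1, so this requires a breach of a stated rule. Smoking is ad libitum, sticks are given on request and logged, and COHb blood goes to a central laboratory (Protocol 7.6). Eligibility and enrolment are settled on Day -3, so selection at entry is not at issue. Sex and consumption stratum are also fixed by Admission; only the four biomarker baselines are exposed. The urinary primaries are creatinine-adjusted concentrations, so an incomplete collection affects them less directly than it affects quantity excreted. All of this stands, and it limits the point to a leak or to staff influence on dispensing, timing or completeness.

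It is also fair that staff knowledge on Day -1 is an inference. Protocol 6.5 gives no start time for unblinding, and the same sentence calls subjects unblinded, which they are not until Day 1. The documents neither state nor prevent early access by staff.

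Two stronger readings do not hold:

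- A reader might conclude that the confirmatory type I error is inflated. The error figures in step 5 belong to a test at 50%, which is the design and evaluation criterion. The written null is a ratio of 1.
- A reader might see an FAS rule that favours one arm, because a CC-arm subject could qualify with a cigarette smoked late on Day -1. That requires product to mean the assigned product, which the text does not say. Read literally, such a cigarette qualifies a subject in either arm. A subject who then leaves has no Day 5 value for the primary model.

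Finally, Day -2 values exist for every primary biomarker and graphs over all timepoints are planned, so a large Day -1 shift in one arm could be noticed. That would help detection but would not prevent the shift.

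**Conclusion.** The point holds as a gap in allocation concealment: the text permits the site to hold the allocation before baseline is complete, and nothing in the conduct described requires this. It does not show that a bias will occur. With no leak and no staff influence the bias is zero.

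If there were one, its size and direction are unknown. Over the assumed range (5 to 20% movement, slope 0.3 to 1.0, transient and in one arm only) the adjusted ratio changes by a factor between 0.985 and 0.833, or between 1.015 and 1.200 in the other direction. The superiority conclusion at the planned ratios is safe. The size of the reported reduction, its CI and its reading against 50% are not fully protected, COHb least of all. This is a worthwhile improvement because it costs almost nothing, and it is no reason to doubt the design as a whole.

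**What to change.** In Protocol 6.4, the Randomization definition, Table 9 and the matching SAP text (section 4 and 6.3.1), state that IxRS releases the allocation to the site only after the last Day -1 assessment and the end of smoking at 11:00 PM, and before the subject is told on Day 1. Require the final Day -1 urine void before the subject is told. Stratification data can be entered earlier, since they are known at Admission.

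Release after 11:00 PM fully protects the COHb baseline. For urine, it leaves only the overnight portion open to staff who know the arm, and the void rule closes the subject's side. With late release, no Day -1 cigarette can count as post-randomisation product use for the FAS.

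The cost is a protocol edit and a release-time setting in IxRS, with no extra subjects or procedures. The downside is that allocations arrive overnight or early in the morning, so products and topography devices for both arms must be ready.

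If conduct can no longer be changed, report the IxRS time stamps and add a sensitivity analysis with the Day -2 values as baseline. These precede the allocation provided the call came after the Day -2 collection ended on the morning of Day -1. Also define FAS product use as use from 06:30 AM on Day 1.
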